#### C.3.6.2 Exclusion Criteria

Subjects are NOT eligible for trial participation if they meet ANY of the following exclusion criteria:

1. Subject has refused surgical aortic valve replacement (SAVR) as a treatment option;
2. Any condition considered a contraindication for placement of a bioprosthetic valve (i.e. subject requires a mechanical valve);

3. A known hypersensitivity or contraindication to all anticoagulation/antiplatelet regimens (or inability to be anticoagulated for the index procedure), nitinol, or sensitivity to contrast media which cannot be adequately pre-medicated;
4. Blood dyscrasias as defined: leukopenia (WBC <1000mm^3), thrombocytopenia (platelet count <50,000 cells/mm^3), history of bleeding diathesis or coagulopathy;
5. Ongoing sepsis, including active endocarditis;
6. Any condition considered a contraindication to extracorporeal assistance;
7. Any percutaneous coronary or peripheral interventional procedure performed within 30 days prior to randomization (Subjects with recent placement of drug eluting stent(s) should be assessed for ability to safely proceed with SAVR within the protocol timeframe);
8. Symptomatic carotid or vertebral artery disease or successful treatment of carotid stenosis within six weeks of randomization;
9. Cardiogenic shock manifested by low cardiac output, vasopressor dependence, or mechanical hemodynamic support;
10. Recent (within 6 months of randomization) cerebrovascular accident (CVA) or transient ischemic attack (TIA);
11. Active gastrointestinal (GI) bleeding that would preclude anticoagulation;
12. Subject refuses a blood transfusion;
13. Severe dementia (resulting in either inability to provide informed consent for the trial/procedure, prevents independent lifestyle outside of a chronic care facility, or will fundamentally complicate rehabilitation from the procedure or compliance with follow-up visits);
14. Multivessel coronary artery disease with a Syntax score >22 and/or unprotected left main coronary artery (Syntax score calculation is not required for patients with history of previous revascularization if repeat revascularization is not planned);
15. Estimated life expectancy of less than 24 months due to associated non-cardiac co-morbid conditions;
16. Other medical, social, or psychological conditions that in the opinion of the Investigator precludes the subject from appropriate consent or adherence to the protocol required follow-up exams;

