17. Currently participating in an investigational drug or another device trial (excluding registries);
18. Evidence of an acute myocardial infarction ≤30 days before the index procedure;
19. Need for emergency surgery for any reason;
20. True porcelain aorta (i.e. Heart Team agrees the aorta is not clampable for SAVR);
21. Extensive mediastinal radiation;
22. Liver failure (Child-C);
23. Reduced ventricular function with left ventricular ejection fraction (LVEF) <20% as measured by resting echocardiogram;
24. Uncontrolled atrial fibrillation (eg. resting heart rate >120bpm);
25. Pregnancy or intent to become pregnant prior to completion of all protocol follow-up requirements;
26. End stage renal disease requiring chronic dialysis or creatinine clearance < 20 cc/min;
27. Pulmonary Hypertension (systolic pressure> 80mmHg);
28. Severe Chronic Obstructive Pulmonary Disease (COPD) demonstrated by Forced Expiratory Volume (FEV1) < 750cc;
29. Frailty assessments identify:
  - Subject is < 80 years of age and three or more of the following apply
  - Subject is ≥ 80 years of age and two or more of the following apply
    - Wheelchair bound
    - Resides in an institutional care facility (eg. nursing home, skilled care center)
    - Body Mass Index < 20 kg/m^2
    - Grip strength <16 kg
    - Katz Index score ≤ 4

- o Albumin < 3.5 g/dL;
- 30. Marfan syndrome or other known connective tissue disease that would necessitate aortic root replacement/intervention.

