**Figure 1: Enrollment Flowchart**

If the patient meets all of the inclusion criteria and none of the exclusion and Heart Team determines the patient is eligible for randomization in the SURTAVI trial, subjects will be randomized on a 1:1 basis to either TAVI or SAVR. Randomization will be stratified by the need for coronary revascularization. In case of required coronary revascularization, concomitant percutaneous coronary intervention (PCI) and TAVI is encouraged; however staging is left at the discretion of the operator. Coronary artery bypass graft (CABG) should be conducted during the index procedure.

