### C.4.5 Enrollment and Randomization

Prior to randomization and enrollment of a subject, the following must occur:

- Confirm patient signed informed consent
- Confirm patient meets all of the inclusion and none of the exclusion criteria, including approval by the Heart Team

Subjects will be considered enrolled into the trial at the time of randomization (i.e. time of treatment assignment). Randomization will occur only if the patient meets all inclusion criteria and does not meet any exclusion criteria and has been assessed by the Heart Team as being an appropriate candidate for randomization in the SURTAVI trial.

Due to the inclusion/exclusion criteria, not all patients that consent to the trial will be enrolled. All sites will be required to maintain a record of patients screened for the trial meeting general inclusion criteria who have signed the approved informed consent document. For subjects that do not meet trial criteria, the reason for not continuing in the trial must be documented and recorded in the EDC system. Patients consented but not randomized will be considered screen failures and no further trial-related follow-up will be required.

Subjects must have their TAVI or SAVR procedure no later than 30 days post-randomization.

Trial randomization will not be blinded. Once randomization is complete and a treatment arm is assigned, crossover from SAVR to TAVI treatment is not permitted. The sponsor will strictly monitor device dispensation to ensure that only those subjects randomized to the TAVI treatment arm receive the Medtronic CoreValve™ or CoreValve™ Evolut™ R TAV.

Distribution of the subjects within the trial groups will be controlled at the implanting sites by means of central randomization using interactive voice/web randomization service (IXRS). The randomization scheme will be securely stored at the IXRS provider.

---

 Based on protocol design, the time of enrollment will be the same as randomization which is a deviation from ISO 14155 (2011).

Randomization with an assignment to the treatment arm or control arm (TAVI or SAVR) will be executed in a 1:1 ratio. Stratified randomization by investigational site and by the need for coronary revascularization will be used to ensure subjects will be allocated to each comparison group proportionately. Additionally, a blocked randomization scheme with random block sizes will be used within each stratum.

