### C.4.7 *Transcatheter Aortic Valve Implant or Surgical Aortic Valve Replacement Procedure*

#### C.4.7.1 TAVI

##### **General Procedural Considerations**

Transcatheter Aortic Valve Implantation (TAVI) requires meticulous preparation and typically a multi-disciplinary team approach involving among others, interventional cardiologists, cardiac imaging specialists, cardio-thoracic surgeons and anesthesiologists.

***Within the United States, additional requirements apply for composition of the intra-operative team for TAVI procedures. Requirements are outlined in Appendix R.25.***

In case of significant coronary artery disease that requires revascularization, the Heart Team will assess the feasibility of performing PCI simultaneously with the TAVI procedure based on the coronary lesion characteristics. When it is anticipated PCI can be performed in timely fashion with only a limited amount of additional contrast medium it is encouraged to perform PCI concomitant with the TAVI. When PCI is deemed challenging requiring relatively more time and contrast medium, staged PCI is recommended: TAVI will then be performed at least 7 days after PCI.

The implantation procedure itself takes place either in a catheterization laboratory with adequate hygiene precautions or ideally in a hybrid operating room equipped for state-of-the-art transcatheter and/or surgical procedures.

The execution of the TAVI involves an operating team typically consisting of 1 or 2 operators, an anesthesia team and at least 2 nurses/technicians. Medtronic representative(s) (eg. Therapy Development Specialists, proctors, etc.) may be present during TAVI procedures for training process, to perform valve loading or to provide general case support.

Both the dedicated “valve team” and the operators should have the expertise to select the appropriate access route and device size on a patient-per-patient basis.

All patients undergoing TAVI should be treated using the iliofemoral access route by default (first treatment strategy). Additional non-iliofemoral access routes will only be used in case iliofemoral access is not feasible. Alternative access is limited to subclavian and direct aortic.

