**Table 3: Schedule of Assessments**

Parameter	Screening	RANDOMIZATION	Baseline	Procedure	Discharge	30 days	3 Months	6 Months	12 Months	18 Months	24 Months	3 – 5 years
			(within 14 days of procedure)									
Informed consent (and in US HIPAA Authorization)	•											
Inclusion/Exclusion	•			•*								
Demographics and Medical history	•											
Physical Examination	•		•		•	•		•	•	•	•	•
Clinical Assessments	•											
NYHA Class	•		•			•		•	•	•	•	•
Risk Assessments: STS Risk Score, Logistic EuroSCORE, EuroSCORE II, SYNTAX Score, and Katz Index	•											
Co-morbidities	•											
Concomitant Medications 			•	•	•	•		•	•	•	•	
Routine Laboratory Tests	•		•	• 	•	• 						
Neurological Assessments  (NIHSS, mRS, MMSE-2:SV and Additional Neurological Assessments) 			•		•				•		•	
Abbreviated Neurological Assessment (NIHSS only)				• 		•		•		•		•
Transthoracic Echocardiogram (TTE)	•			• 				•	•		•	•
Computed Tomography (CT) Angiogram (MSCT required at screening) 	•											
Coronary Arteriogram	•			(•)								
Aortogram				(•)								
12-lead Electrocardiogram	•		•	• 	•	•		•	•	•	•	•
6 Minute Walk Test			•			•			•		•	
Quality of Life Questionnaires (EQ-5D, KCCQ, and SF-36)			• 			•	• 	•	•	•	•	•
Adverse Events			•	•	•	•		•	•	•	•	• 

- \* Document any changes to subject condition that affect inclusion/exclusion criteria, confirm the subject does not meet any exclusion criteria specific to the Index Procedure (eg. percutaneous coronary or peripheral intervention and evidence of an acute myocardial infarction which must not occur within 30 days prior to the index procedure)
- (•) TAVI subjects only (SAVR subjects will not have these assessments)
  -  Laboratory test results must be performed pre-procedure and CK to be obtained within 8-12 hours post-procedure
  -  Pre-procedure
  -  Only hemoglobin, creatinine and creatinine clearance are required to be collected
  -  Electrocardiogram within 48 hours post-procedure
  -  TTE to be completed at least 24hours post-procedure but prior to discharge (and no later than 7 days post procedure) to assess device success

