Prior approval by the sponsor is expected in those situations in which the Investigator anticipates, contemplates or makes a conscious decision to depart from procedures specified in the protocol. Prior approval is generally not expected in situations where unforeseen circumstances are beyond the Investigator's control, but is still considered a deviation (eg. a trial subject who fails to attend a scheduled follow-up visit, a trial subject too ill to perform a protocol-required test). To obtain approval, the Investigator must call or email and discuss the potential deviation with the Medtronic trial manager or designee prior to initiating any changes. If approval is granted, the Medtronic trial manager or designee will provide the applicable documentation to be maintained in the site files.

FDA regulations require the Investigator to notify the sponsor and the reviewing IRB/MEC within 5 working days of the following deviations [21 CFR 812.150]:

- a deviation from protocol to protect the life or physical wellbeing of a patient in an emergency
- failure to obtain an informed consent

Investigators or an authorized designee must notify Medtronic as soon as possible by calling the trial manager or designee and completing the protocol deviation form.

The Investigator is required to adhere to local IRB/MEC procedures for reporting deviations.

The DSMB may review protocol deviations to ensure compliance and overall trial integrity.

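### The Table 3 procedure-day check puts PCI under a 30-day bar that contradicts exclusion 7 and C.4.7.1, leaving no compliant TAVI date after a staged PCI done after randomization

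*Combined protocol and SAP*

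**What the plan says.** Two exclusion criteria in C.3.6.2 use a 30-day window with different anchors. Exclusion 7 counts back from randomization: "Any percutaneous coronary or peripheral interventional procedure performed within 30 days prior to randomization". Exclusion 18 counts back from the procedure: "Evidence of an acute myocardial infarction ≤30 days before the index procedure".

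The starred footnote to Table 3 (C.4.13) adds a check at the procedure visit. Sites are to document changes in the subject's condition and "confirm the subject does not meet any exclusion criteria specific to the Index Procedure". The examples given are "percutaneous coronary or peripheral intervention and evidence of an acute myocardial infarction which must not occur within 30 days prior to the index procedure".

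C.4.5 sets the outer limit: "Subjects must have their TAVI or SAVR procedure no later than 30 days post-randomization".

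For TAVI subjects who need revascularization, the text under Figure 1 (C.3.9) encourages PCI in the same session but adds that "staging is left at the discretion of the operator". C.4.7.1 goes further for challenging lesions: "staged PCI is recommended: TAVI will then be performed at least 7 days after PCI". Under C.3.9 and C.4.7.2, revascularization in the SAVR arm is bypass grafting at the index operation.

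**The concern.** The footnote reads as a restatement of existing exclusions, but it moves the PCI window from randomization to the index procedure. That puts an operative check, made just before treatment, in conflict with the eligibility criterion it appears to restate and with a treatment path that the protocol recommends.

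The subjects concerned are foreseen by design, because need for revascularization is a randomization stratum (C.4.5, C.6.5.2). A site that applies the footnote literally would flag a TAVI subject with a staged PCI as failing eligibility on the procedure day. If no procedure is then attempted, C.6.4.2 removes the subject from the mITT population, which is the primary analysis set. Any such loss would fall on the TAVI arm only, since staged PCI does not arise in the SAVR arm. A site that ignores the footnote and follows C.4.7.1 treats the subject but leaves a failed check on record. Sites may differ in which text they follow.

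**Working it through.** The plan states no figure to reproduce here; the check is one of calendar dates. Day 0 is randomization, *p* the day of PCI, *m* the day of MI, *t* the day of the index procedure.

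**Inputs**
- C.4.5: *t* ≤ 30.
- C.4.7.1: *t* − *p* ≥ 7 for a staged PCI.
- Table 3 footnote: intervention or MI within 30 days before the procedure is barred, so *t* − *p* > 30 and *t* − *m* > 30 are needed.
- Exclusion 7: no PCI in the 30 days before randomization. This says nothing about *p* ≥ 0.
- Exclusion 18: *t* − *m* > 30.

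**Staged PCI after randomization**
1. Under C.4.7.1 and C.4.5 alone, *t* runs from *p* + 7 to 30, which gives 24 − *p* days. For *p* = 0 that is days 7–30 (24 days), for *p* = 10 days 17–30 (14 days), and for *p* = 23 day 30 only (1 day). Later PCI leaves no date.
2. Total allowed pairs: 24 + 23 + … + 1 = 24 × 25 / 2 = 300.
3. The longest possible gap is 30 − 0 = 30 days. The footnote needs more than 30, so 0 of 300 pairs remain.
4. If the bar is read as fewer than 30 days, a gap of exactly 30 passes. Only PCI on day 0 with TAVI on day 30 survives: 1 of 300.

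The footnote alone bars only gaps of 30 days or less. It takes the day-30 limit in C.4.5 as well to remove every post-randomization staged PCI. A PCI more than 30 days before randomization passes both exclusion 7 and the footnote, but it is not the staged PCI of a subject already assigned to TAVI.

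**MI around randomization (for the optional clarification)**
1. For an MI on day *m* ≥ 0, the first date exclusion 18 allows is *m* + 31: day 31 for *m* = 0, day 41 for *m* = 10, day 60 for *m* = 29. All are past day 30, so no date meets both rules.
2. For an MI *d* days before randomization (*d* = 1 to 30), days 31 − *d* to 30 comply: day 30 only for *d* = 1, days 21–30 for *d* = 10, days 1–30 for *d* = 30. These subjects have a compliant date.
3. The documents give no MI rate for the waiting period. Assuming 0.2–0.5%, with 1600 / 2 = 800 subjects per arm, 1.6–4 subjects per arm would be affected. At the planned 17% rate an arm has 136 events. Suppose the affected subjects go untreated in one arm only and 40–100% of them would have had a primary event:
   - Smallest case: (136 − 1.6 × 0.4) / 798.4 = 16.95%, a fall of 0.05 points.
   - Largest case: (136 − 4) / 796 = 16.58%, a fall of 0.42 points, or 6% of the 7-point margin.
   - Equal losses in both arms would cancel.

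**The case against.** On PCI, the best defence is that the footnote offers examples rather than a new criterion, and that the operative texts (exclusion 7, C.3.9 and C.4.7.1) agree with one another. On this view the footnote is a slip that a sensible site would read past. It is indeed a wording error with a narrow reach. But it is an instruction to confirm something on the procedure day, and nothing in the text tells a site which rule prevails. One could also parse the 30-day clause as applying to MI alone. Even then the footnote lists PCI among exclusions specific to the index procedure, which exclusion 7 is not.

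On MI, a reader might infer that exclusion 18 and C.4.5 contradict each other and that subjects with an MI while waiting are bound to go untreated and bias the primary analysis. The documents do not support that. Exclusion 18 is deliberately anchored to the procedure and deliberately re-checked, so withholding a within-protocol procedure from a subject with a fresh MI is the exclusion doing its job. The outcome is also provided for:
- C.4.9 sets follow-up from day 31 for subjects never attempted.
- C.6.4.2 keeps them in ITT and plans an ITT analysis.
- C.4.18 and Table 6 give deviation routes ("Prior approval by the sponsor is expected in those situations in which the Investigator anticipates, contemplates or makes a conscious decision to depart").
- A subject treated late remains in mITT, which has no time window.

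An automatic extension of the day-30 limit would also be clinically incomplete. An MI can newly trigger other exclusions, such as cardiogenic shock, a Syntax score above 22, or an ejection fraction below 20%. A longer wait also lengthens the period in which a death before any attempt falls outside mITT. What stands on MI is only that the text reviewed (part 2 of 4) has no specific instruction.

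**Conclusion.** The PCI wording in the Table 3 footnote is wrong as written. It conflicts with exclusion 7 and with the staging rules in C.3.9 and C.4.7.1. With the day-30 limit it leaves 0 of 300 otherwise allowed date pairs, or 1 of 300 on the most lenient reading of the window. This rests on reading the 30-day clause as covering both examples, which is its natural sense.

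The reach is limited to TAVI-arm subjects who need staged revascularization. The pair counts show that the rules cannot all be met; they do not measure how many subjects are affected, and no direction or size of bias is shown. It would be too strong to say that the footnote by itself forbids staged PCI, or that it threatens the primary result.

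The MI timing is a gap in instruction that the sponsor may choose to close. Under the assumptions shown, its effect on the primary comparison would be small.

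**What to change.** Reword the starred footnote to Table 3 so that:
- the procedure-day re-check with a 30-day bar applies to acute MI only (exclusion 18);
- PCI and peripheral intervention follow exclusion 7, counted back from randomization;
- planned staged PCI follows C.4.7.1, with TAVI at least 7 days after PCI and within the C.4.5 limit.

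This is a wording correction to one footnote. Exclusions 7 and 18, the analysis populations, the sample size and the decision thresholds stay as they are.

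Optionally, add to C.4.5 that after an MI between randomization and procedure the Heart Team re-reviews the subject. If continued eligibility is confirmed, the procedure may be done after day 30 in the assigned arm. The day-31 follow-up anchor in C.4.9, which is defined as the first day after the 30-day window, must then be adjusted to match for a subject who is granted the extension but never treated. The cost is a few later procedures and a longer exposure to events before any attempt. Whether that trade is worth making, and how long the extension should be, is for the sponsor's clinicians.

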**Anatomical Exclusion Criteria**

- 31. Native aortic annulus size <18 mm or >29 mm per the baseline diagnostic imaging;
- 32. Pre-existing prosthetic heart valve in any position;
- 33. Mixed aortic valve disease [aortic stenosis and aortic regurgitation with predominant aortic regurgitation (3-4+)];
- 34. Severe mitral or severe tricuspid regurgitation;
- 35. Severe mitral stenosis;
- 36. Hypertrophic obstructive cardiomyopathy;
- 37. Echocardiographic or Multislice Computed Tomography (MSCT) evidence of new or untreated intracardiac mass, thrombus or vegetation;
- 38. Ascending aorta diameter greater than maximum diameter relative to the native aortic annulus size:

Aortic Annulus Diameter	Ascending Aorta Diameter
18 mm – 20 mm	>34 mm
20 mm – 23 mm	>40 mm
23 mm – 29 mm	>43 mm

- 39. Aortic root angulation (angle between plane of aortic valve annulus and horizontal plane/vertebrae):
  - a) Femoral and left subclavian/axillary access > 70°

**OR**

  - b) Right subclavian/axillary access: Aortic root angulation > 30°;
- 40. Congenital bicuspid or unicuspid valve verified by echocardiography;
- 41. Sinus of Valsalva anatomy that would prevent adequate coronary perfusion.

**Vascular Exclusion Criteria**

- 42. Transarterial access not able to accommodate an 18Fr sheath.

### C.3.7 *Informed Consent*

The investigator must obtain written informed consent prior to subjecting the subject to any trial related activity.

Well in advance of the consent discussion, the subject should receive the MEC/IRB approved Patient Information and Informed Consent Form (ICF). During the consent discussion the investigator or his/her designee must fully inform the subject of all pertinent aspects of the trial including the approval of the MEC/IRB of the written Patient Information. If a subject is illiterate, an impartial witness must be present during the entire informed consent discussion. All items discussed in the Patient Information and the ICF must be explained. The language used shall be in the subject's native language, as non-technical as possible and must be understandable to the subject and the impartial witness, where applicable.

The subject must have ample time and opportunity to inquire about details of the trial, and to decide whether or not to participate in the clinical trial. All questions about the trial should be answered to the satisfaction of the subject.

Neither the investigator, nor the investigation site staff shall coerce or unduly influence a subject to participate or to continue to participate in the clinical trial. The informed consent process shall not appear to waive the subject's rights.

When the subject decides to participate in the clinical trial, the ICF must be signed and personally dated by the subject and investigator. If applicable, the witness shall also sign and personally date the consent form to attest that the information in the Patient Information and Informed Consent Form was accurately explained and clearly understood by the subject, and that informed consent was freely given.

Signing the ICF serves to document the written and verbal information that the Investigator or authorized delegate provides to the patient, the patient understanding of the information, and their agreement to participate. The Investigator or authorized delegate must document in the patient's medical records that the patient was consented and the date on which the consent was obtained. The original signed consent form will be retained in the patient's trial records. A copy of the informed consent will be provided to the patient and a copy placed in the patient's medical record.

Data relating to the trial might be made available to third parties (for example in case of an audit performed by regulatory authorities), provided the data are treated as confidential and that the subject's privacy is guaranteed. In the United States, "Protected Health Information" will be maintained in compliance with the Health Insurance Portability and Accountability Act of 1996 (HIPAA).

[figure not shown]
